10.3.3.1 Multiplicity Adjustment

Multiplicity adjustments will be generated based on Off-treatment Hypothetical Estimand Population for Europe. The multiplicity adjustments will be applied to primary endpoint and the European set of the Secondary efficacy endpoints listed in Table 10.1-1.

The overall graphic approach procedure for primary and secondary efficacy endpoints for Europe is defined in the Table 10.3-2 and Figure 10.3-1.

[figure not shown]
The initial allocation of the overall significant level to 2 primary hypotheses will be 1/2 of the overall significance level for each dose, and no initial α is allocated to the hypotheses for secondary endpoints.

Within each individual dose, testing will start from the primary endpoint, and then test the secondary endpoints in a prespecified order. The order of testing for the first three secondary endpoints is determined by the power of individual endpoints based on the results from Phase 2/3 study CGP-MD-01. Endpoints related to HIT-6 and MSQ v2.1 are placed in the last two positions in the testing hierarchy. If the null hypotheses for both the primary and the first three secondary endpoints are rejected for one of the doses, 1/3 of the associated alpha is passed to the other dose to increase the chances of success for the other dose in testing endpoints in the primary positions of the hierarchy, and the remaining 2/3 of the associated alpha is reserved for testing HO endpoints within the same dose. If hypotheses for two HO endpoints are rejected within a dose based on remaining alpha, the alpha for this dose will be propagated to the other dose to make full use of the alpha.

Table 10.3-2. Multiple Comparisons Procedure Definitions for EU Filing

Nodes	Alternate Hypothesis	Weight	Initial Local Significance Level
30mgBID P1	30 mg BID atogepant is significantly different from placebo in change from baseline in mean monthly migraine days across the 12-week treatment period (P1)	1/2	$\alpha \times (1/2) = \alpha/2$
60mgQD P1	60 mg QD atogepant is significantly different from placebo in change from baseline in mean monthly migraine days across the 12-week treatment period (P1)	1/2	$\alpha \times (1/2) = \alpha/2$
30mgBID S1	30 mg BID atogepant is significantly different from placebo in change from baseline in mean monthly headache days across the 12-week treatment period (S1)	0	$\alpha \times 0 = 0$
60mgQD S1	60 mg QD atogepant is significantly different from placebo in change from baseline in mean monthly headache days across the 12-week treatment period (S1)	0	$\alpha \times 0 = 0$
30mgBID S2	30 mg BID atogepant is significantly different from placebo in change from baseline in mean monthly acute medication use days across the 12-week treatment period (S2)	0	$\alpha \times 0 = 0$
60mgQD S2	60 mg QD atogepant is significantly different from placebo in change from baseline in mean monthly acute medication use days across the 12-week treatment period (S2)	0	$\alpha \times 0 = 0$
30mgBID S3	30 mg BID atogepant is significantly different from placebo in proportion of participants with at least a 50% reduction in 3-month average of monthly migraine days (S3)	0	$\alpha \times 0 = 0$
60mgQD S3	60 mg QD atogepant is significantly different from placebo in proportion of participants with at least a 50% reduction in 3-month average of monthly migraine days (S3)	0	$\alpha \times 0 = 0$
30mgBID S4	30 mg BID atogepant is significantly different from placebo in change from baseline in the HIT-6 total score at Week 12 (S4)	0	$\alpha \times 0 = 0$
60mgQD S4	60 mg QD atogepant is significantly different from placebo in change from baseline in the HIT-6 total score at Week 12 (S4)	0	$\alpha \times 0 = 0$
30mgBID S5	30 mg BID atogepant is significantly different from placebo in change from baseline in MSQ v2.1 Role Function-Restrictive domain score at Week 12 (S5)	0	$\alpha \times 0 = 0$
60mgQD S5	60 mg QD atogepant is significantly different from placebo in change from baseline in MSQ v2.1 Role Function-Restrictive domain score at Week 12 (S5)	0	$\alpha \times 0 = 0$

Figure 10.3-1. Multiple Comparisons Procedure for Europe and Canada

10.3.4 Additional Efficacy Endpoints and Health Outcomes Analysis

In general, all additional efficacy endpoint analyses are performed at the nominal significance level, without adjusting for multiplicity and will be based on the Off-treatment Hypothetical Estimand Population.

The additional endpoints are described in Section 10.1.3 and the analysis methods are the same with those analysis methods in support of US filing, which are described in Section 10.2.3.

10.4 EFFICACY ANALYSIS FOR HEALTH CANADA

10.4.1 Primary Efficacy Analysis

The primary efficacy analyses in support of Canadian filing will be based on the mITT Population. The primary endpoint, change from baseline in mean monthly migraine days across the 12-week treatment period, will be analyzed in the same manner as that used to analyze the primary endpoint in support of US filing.

10.4.2 Secondary Efficacy Analysis

The secondary efficacy analyses will be based on the mITT Population.

The secondary efficacy endpoints are listed in the Table 10.1-1. All secondary endpoints will be handled using the same approaches defined in the Section 10.2.2. The analysis of HIT-6 total score is similar to that of MSQ v2.1 role function restrictive domain score.

Multiplicity adjustments will be generated based on mITT population and will be generated based on primary and the Canadian set of secondary efficacy endpoints listed in the Table 10.1-1. The overall graphic approach procedure for primary and secondary efficacy endpoints for Canada is the same with that used in the Section 10.3.3.

10.4.3 Additional Efficacy Endpoints and Health Outcomes Analysis

In general, all additional efficacy endpoint analyses are performed at the nominal significance level, without adjusting for multiplicity and will be based on the mITT Population.

The additional endpoints are described in Section [10.1.3](#) and the analysis methods are the same with those analysis methods in support of US filing, which are described in Section [10.2.3](#).

11.0 SAFETY ANALYSES

The safety analysis will be performed using the Safety Population. The safety parameters will include adverse events (AEs), clinical laboratory, vital sign, electrocardiographic (ECG), and C-SSRS. For each safety parameter of the clinical laboratory, vital sign, and ECG, the last nonmissing safety assessment before the first dose of study treatment will be used as the baseline for all analyses of that safety parameter. Continuous variables will be summarized by number of participants and mean, SD, median, Q1, Q3, minimum, and maximum values. Categorical variables will be summarized by number and percentage of participants.

11.1 ADVERSE EVENTS

Adverse events will be coded by system organ class and preferred term using the *Medical Dictionary for Regulatory Activities (MedDRA)*, version 21.1.

An AE will be considered as a treatment-emergent adverse event (TEAE) if the AE began or worsened (increased in severity or became serious) on or after the date of the first dose of double-blind study treatment. However, an AE that occurs more than 30 days after the last dose of double-blind study treatment or Visit 8 whichever comes later will not be counted as a TEAE. Per case report form instructions, a new AE record will be created with a new AE onset date for any AE that worsens. Therefore, TEAEs can simply be identified as those AEs with recorded onset date on or after the date of the first dose of double-blind study treatment and within 30 days after the last dose of double-blind study treatment or Visit 8 whichever comes later. TEAEs that started after the date of last dose of study treatment will be considered as newly emergent.

Only AEs captured in study 3101-303-002 will be considered for TEAEs in this study. For participants rolling over into studies 3101-306-002, 3101-311-002 or 3101-312-002 (extension studies) who start the first dose on Visit 1 or beyond, AEs captured in those studies will be summarized in those studies although some AEs might occur within 30 days after the last dose from study 3101-303-002.

Overall summary of AEs will be provided on a per-participant basis for categories of TEAEs, treatment-related TEAEs, serious adverse events (SAEs), deaths, and AEs leading to study intervention discontinuation.

The number and percentage of participants reporting TEAEs in each treatment group will be tabulated by descending percentage in Atogepant 60 mg QD group, by system organ class and preferred term, and further categorized by severity and causal relationship to the study treatment. If more than 1 AE is coded to the same preferred term for the same participant, the participant will be counted only once for that preferred term using the greatest severity and strictest causality for the summarization by severity and causal relationship.

For “current use” of migraine prevention medication participants, the number and percentage of participants reporting TEAEs in each treatment group will be tabulated by system organ class and preferred term.

The number and percentage of participants reporting newly emergent TEAEs in each treatment group will be tabulated by system organ class and preferred term for the safety follow-up period.

The total number of TEAEs by severity and causal relationship to the study treatment will be summarized by treatment group.

The incidence of common ($\geq 2\%$ of participants [after rounding] in any treatment group) TEAEs will be summarized by preferred term and treatment group and sorted by decreasing frequency in the Atogepant 60 mg QD group. A similar 5% table will be provided as well.

An AE will be considered a treatment-emergent serious adverse event (TESAE) if it is a TEAE that additionally meets any SAE criterion.

The number and percentage of participants who have TESAEs will be summarized by system organ class and preferred term by treatment group. In addition, the incidence of on-therapy SAEs that led to death will be summarized separately by preferred term for each treatment group.

The number and percentage of participants in the Safety Population who have TEAEs and TESAEs leading to premature discontinuation of the study intervention will be summarized by system organ class, preferred term and treatment group.

The number and percentage of participants reporting newly emergent SAEs and those that led to death will be summarized respectively by preferred term and treatment group for the safety follow-up period.

For all screened participants, separate tabular displays will be presented for participants who died, participants with SAEs, and participants with AEs leading to study intervention discontinuation.

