16.0 DATA HANDLING CONVENTIONS

16.1 VISIT TIME WINDOWS

For analysis purposes, Day 1 is defined as the date of the first dose of double-blind study intervention. On-treatment Period is defined as from the first dose till the last dose.

The analysis visit windows for monthly efficacy endpoints based on daily eDiary data for mITT Population are defined as follows.

Table 16.1-1. Efficacy Analysis Visit Definitions for eDiary Data

Analysis Phase	Analysis Visit (Derived)	eDiary Window
Pretreatment	Baseline	The last 28 days prior to randomization
Double-Blind Treatment Period	Weeks 1 – 4	Treatment Day [1, 28]
	Weeks 5 – 8	Treatment Day [29, 56]
	Weeks 9 – 12	Treatment Day [57, min (end of the double-blind treatment period, 84)]

The analysis visit windows for monthly efficacy endpoints based on daily eDiary data for Off-treatment Hypothetical Estimand Population are defined as follows.

Table 16.1-2. Efficacy Analysis Visit Definitions in the Off-treatment Hypothetical Estimand Approach for eDiary Data

Analysis Phase	Analysis Visit (Derived)	eDiary Window
Pretreatment	Baseline	The last 28 days prior to randomization
On or after the first dose of study intervention	Weeks 1 – 4 (on/off study treatment)	Days [1, 28]
	Weeks 5 – 8 (on/off study treatment)	Days [29, 56]
	Weeks 9 – 12 (on/off study treatment)	Days [57, min(end of the last visit, 84)]

Day 1 = the date of the first dose of double-blind study intervention.

The analysis visit windows for weekly efficacy endpoints in the first monthly period based on daily eDiary data for mITT Population are defined as follows.

Table 16.1-3. Efficacy Analysis Visit Definitions for eDiary Data in the First Monthly Period

Analysis Phase	Analysis Visit (Derived)	eDiary Window
Pretreatment	Baseline	The last 28 days prior to randomization
Double-Blind Treatment Period	Week 1	Treatment Day [1, 7]
	Week 2	Treatment Day [8, 14]
	Week 3	Treatment Day [15, 21]
	Week 4	Treatment Day [22, 28]

The analysis visit windows for daily efficacy endpoints in the first weekly period based on daily eDiary data for mITT population are defined as follows:

Table 16.1-4. Efficacy Analysis Visit Definitions for eDiary Data

Analysis Phase	Analysis Visit (Derived)	eDiary Window
Pretreatment	Baseline	The last 28 days prior to randomization
Double-blind treatment period	Initial Dose Day	Treatment Day 1
	1 Day after Initial Dose	Treatment Day 2
	2 Days after Initial Dose	Treatment Day 3
	3 Days after Initial Dose	Treatment Day 4

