End of Double-blind Treatment Period is defined as the last available assessment during double-blind treatment period. End of Double-blind Treatment Period results will be presented in analysis tables for clinical laboratory values and vital signs.

End of Study is defined as the last available assessment during the study, including double-blind and safety follow-up period.

End of Study results will be presented in analysis tables for safety parameters, including but not limited to electrocardiograms, clinical laboratory values, and vital signs.

ET = early termination.

For endpoints collected by visit (not for eDiary data), if a participant has 2 or more visits within the same window, the last visit with a non-missing value will be used for analysis, unless specified otherwise.

The following algorithm is used to define the double-blind treatment period and the follow-up periods unless specified otherwise. The double-blind treatment period starts with the date of the first dose of double-blind study treatment and ends with the latest date of the last study medication date, and the last scheduled assessment date of Visit 2 to Visit 7 for participants who entered the safety follow-up period; or ends with the latest date of the last study medication date, and last assessment date for participants who did not enter the safety follow-up period. The safety follow-up period starts with the 1 day after the end of the double-blind period and ends with the last scheduled assessment date of Visit 8 for participants who entered the estimand follow-up period;

or ends with the last assessment date for participants who did not enter the estimand follow-up period. The estimand follow-up period starts with the 1 day after the end of the safety follow-up period and ends with the last assessment date for participants who entered the estimand follow-up period.

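### SAP 11.1 defines newly emergent AEs from the last dose but tabulates them only for a follow-up period that can start later or not exist, so the off-drug tables undercount

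*SAP*

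**What the plan says.** SAP 11.1 counts an AE as treatment-emergent from the first dose and "within 30 days after the last dose of double-blind study treatment or Visit 8 whichever comes later". Within that window it defines an off-drug subset by onset: "TEAEs that started after the date of last dose of study treatment will be considered as newly emergent".

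The tables for that subset carry a further condition. SAP 11.1 says that "newly emergent TEAEs in each treatment group will be tabulated by system organ class and preferred term for the safety follow-up period". For serious and fatal events, "newly emergent SAEs and those that led to death will be summarized respectively by preferred term and treatment group for the safety follow-up period". A separate fatal-event table uses another term: "the incidence of on-therapy SAEs that led to death will be summarized separately by preferred term". On-therapy is not defined.

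SAP 16.1 supplies the periods. The safety "follow-up period starts with the 1 day after the end of the double-blind period". For participants who entered safety follow-up, the double-blind period "ends with the latest date of the last study medication date, and the last scheduled assessment date of Visit 2 to Visit 7". For those who did not, it runs to the later of the last medication date and the last assessment, and no safety follow-up period is set for them. These rules apply unless something else is specified. The same section also says: "On-treatment Period is defined as from the first dose till the last dose".

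**The concern.** The definition and the table use different dates. Newly emergent status begins the day after the last dose; the table begins the day after the double-blind period ends. The two agree only when no Visit 2 to 7 assessment falls after the last dose and the participant enters follow-up. Otherwise an event can be newly emergent by definition and absent from every newly emergent table.

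At stake is the accuracy of the tables meant to show what happens off drug. The data should exist: Protocol 9.1.1 and 9.3 collect AEs and SAEs to Visit 8, or to 30 days after the last dose if Visit 8 is not done. A programmer following SAP 11.1 must choose between the two dates, and the choice changes the counts.

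**Working it through.** No sample size, power or event figure in the plan bears on this point, so there is nothing to reproduce. The check applies the date rules to example participants.

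**Rules**
- TEAE cut-off = max(last dose + 30, Visit 8), the reading used here; without Visit 8, last dose + 30 (SAP 11.1).
- Newly emergent: last dose < onset ≤ cut-off (SAP 11.1).
- Double-blind end = max(last dose, last Visit 2–7 assessment) if follow-up was entered, otherwise max(last dose, last assessment) (SAP 16.1).
- Safety follow-up = double-blind end + 1 up to Visit 8 for those who then enter estimand follow-up (SAP 16.1).

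**Cases** (study days, chosen for illustration; all onsets are newly emergent)

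| Case | Last dose | Visit 7/ET or last assessment | Visit 8 | Onset | Follow-up starts | In off-drug table |
|---|---|---|---|---|---|---|
| a. Completer | 84 | 87 | 112 | 86 | 88 | No |
| b. Completer dosed on Visit 7 day | 85 | 85 | 113 | 86 | 86 | Yes |
| c1. Early stopper | 30 | 40 | 58 | 35 | 41 | No |
| c2. Same participant | 30 | 40 | 58 | 45 | 41 | Yes |
| d1. No follow-up | 30 | 28 | none | 33 | none | No |
| d2. No follow-up | 30 | 37 | none | 34 | none | No |
| e. Estimand follow-up | 20 | 22 | 48 | 49 | 23 | No |

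In case e the cut-off is max(20 + 30, 48) = 50, so Day 49 is a TEAE, but safety follow-up ended on Day 48. This part is narrow: with Visit 8 at 28 days after the last dose, only 30 − 28 = 2 days are exposed.

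**Length of the gap.** Days omitted = Visit 7/ET date − last dose date.
- Completers: Visit 7 is Day 84 with a window of +3 days, preferably not before Day 85 (Protocol Table 1). With the last dose on Day 84, the gap is 85 − 84 = 1 to 87 − 84 = 3 days. With dosing on the day of Visit 7 it is 0.
- Early stoppers: Protocol 8.8 puts Visit 8 four weeks after the last dose. Neither 8.8 nor 8.8.1 gives a deadline for the ET visit.

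As a share of a 28-day off-drug interval: 1/28 = 3.6%, 3/28 = 10.7%. If the ET visit came 7 or 14 days after the last dose, the shares would be 7/28 = 25% and 14/28 = 50%. Those two gaps are assumptions; the documents give no distribution.

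**Fatal SAEs.** Take a fatal SAE starting between the last dose and the ET visit, as in c1.
- If on-therapy means first to last dose, it is in neither fatal-SAE table.
- If on-therapy means the double-blind treatment period, Day 35 falls before its end on Day 40 and the event is in the on-therapy table.

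For a fatal SAE in a participant who never enters follow-up, the second reading helps only if an assessment is dated on or after onset. In d2 the double-blind period ends on max(30, 37) = Day 37, which covers Day 34. In d1 it ends on max(30, 28) = Day 30, which does not cover Day 33. SAP 16.1 does not say whether an AE or death record counts as an assessment.

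**The case against.** The strongest reply is that nothing goes missing. Every event above is a TEAE, so it is in the main TEAE table by SOC and preferred term, with severity and causality. If serious, it is also in the TESAE table and the display of participants with SAEs; if fatal, in the overall summary and the display of deaths. This stands. A reader might infer that off-drug events or deaths vanish from reporting, and SAP 11.1 does not support that.

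Other limits also stand:
- For completers the gap can be zero. Protocol 6.3 and 8.4.2.3 time the Visit 7 PK sample after a morning dose, so consenting participants are expected to dose that day.
- A reader might conclude that early stoppers lose a quarter to a half of their off-drug interval. That rests on assumed ET delays.
- A reader might conclude that the two fatal-SAE tables certainly miss deaths between the last dose and ET. That holds only on one reading of on-therapy.
- It is tempting to say the omitted days are when withdrawal or rebound would show. Neither document states such an aim, and the AEs of special interest in Protocol 6.5.2 concern suicidality and liver tests.
- Rollover participants are exempt from Visit 8, and AEs captured in the extension studies are reported there. Many therefore have little off-drug time in this study to lose.

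Two defences do not succeed. The allowance in SAP 16.1 for other specifications does not close the gap, because SAP 11.1 names no other period and uses the same period label. SAP 4.0 places table specifications in a separate document, but the SAP's own wording would still conflict with a specification that used the last-dose date.

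**Conclusion.** The mismatch is real, and its effect is small. Followed as written, SAP 11.1 and 16.1 leave three groups of newly emergent events out of the newly emergent tables: onset after the last dose but on or before Visit 7/ET; any off-drug AE recorded in this study for participants who never enter safety follow-up; and TEAEs in the estimand follow-up period. The result is an undercount of off-drug events in supplementary tables. Overall TEAE and TESAE rates, the death count and efficacy results do not change.

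For participants who enter follow-up, the undercount before follow-up starts covers 0 to about 3 days for completers and an unknown number for early stoppers. For non-entrants it covers all off-drug AEs recorded in this study. The conclusion assumes that safety follow-up in SAP 11.1 carries its SAP 16.1 meaning. The fatal-SAE hole between the last dose and ET is conditional on on-therapy meaning first to last dose. The number of affected events cannot be estimated from the documents.

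**What to change.** In SAP 11.1, for newly emergent TEAEs, SAEs and SAEs leading to death, replace the restriction to the safety follow-up period with: *with onset after the last dose of study treatment up to the TEAE cut-off, whether or not the participant entered safety follow-up*.

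Alongside it:
- State the Safety Population as the denominator.
- Keep the rule that AEs captured in the extension studies are reported there, and footnote that off-drug observation is shorter for rollover participants.
- Define on-therapy as onset from the first to the last dose. The two fatal-SAE tables then together cover every treatment-emergent fatal SAE. The same cannot be promised for TEAEs in general, because the SAP has no on-drug TEAE table.

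The cost is a wording change and one onset-date condition in the AE program, using data already collected. A few events are added to the supplementary tables. The drawback is that off-drug observation time differs between participants, so these percentages need the footnote to be read correctly.
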